3.7.2. Baseline Characteristics

Baseline characteristics (including demographics, physical measurements, disease history and prior anti-cancer therapies) are described in [Section 6.5.1](#). These baseline characteristics are not planned to be included as stratification variables or covariates in statistical models unless otherwise specified in [Section 6](#).

3.8. Safety Endpoints

3.8.1. Adverse Events

Treatment-Emergent Adverse Events

Treatment-emergent adverse events (TEAEs) are those events with onset dates occurring during the on-treatment period for the first time, or if the worsening of an event is during the on-treatment period.

On-treatment period is defined as the time from the first dose of study treatment through minimum (30 days + last dose of study treatment, start day of new anti-cancer drug therapy – 1 day). The start day of new anti-cancer drug therapy after the first dose of study treatment is derived as outlined in [Section 5.2.5](#).

4. ANALYSIS SETS

Data for all patients will be assessed to determine if patients meet the criteria for inclusion in each analysis population prior to releasing the database and classifications will be documented per Pfizer's standard operating procedures.

Only patients who signed informed consent will be included in the analysis sets below.

4.1. Full Analysis Set

For the randomized cohorts: The full analysis set (FAS) will include all randomized patients. Patients will be classified according to the treatment assigned at randomization.

For non-randomized cohorts: The FAS will include all patients who receive at least one dose of study drug. Patients will be classified according to the study treatment actually received. If a patient receives more than one treatment the patient will be classified according to the first treatment received.

4.2. Safety Analysis Set

For the randomized cohorts: The safety analysis set will include all patients who receive at least one dose of study drug. Patients will be classified according to the treatment assigned at randomization unless the incorrect treatment(s) was/were received throughout the dosing period in which case patients will be classified according to the first study treatment received.

For non-randomized cohorts: The safety analysis set will include all patients who receive at least one dose of study drug. Patients will be classified according to the study treatment actually received. If a patient receives more than one study treatment, the patient will be classified according to the first treatment received. For the non-randomized cohorts of the study, the FAS and the safety analysis set are identical.

4.3. Other Analysis Set

4.3.1. DLT-evaluable Set

The DLT-evaluable set is a subset of the safety analysis set, and it includes all patients who receive at least 1 dose of study treatment (for Portion A: at least 1 dose of PF-05082566; for Portion B: at least 1 dose of PF-05082566 and 1 dose of rituximab). Note that every patient will contribute to the determination of the MTD including patients who are lost to follow up prior to completion of the 2 cycles' DLT observation period.

4.3.2. PK Analysis Set

The PK concentration population is defined as all treated patients (subset of the safety analysis set) who have at least 1 concentration.

The PK parameter analysis population is defined as all treated patients (subset of the safety analysis set) who have at least 1 of the PK parameters of interest.

CCI

4.3.4. Immunogenicity Analysis Set

The immunogenicity analysis set is a subset of the safety analysis set and will include patients who have at least one ADA/Nab sample collected for either PF-05082566 or rituximab.

CCI

5. GENERAL METHODOLOGY AND CONVENTIONS

5.1. Hypotheses and Decision Rules

5.1.1. Hypotheses and Sample Size Determination

No formal statistical hypothesis testing is planned.

The sample sizes planned for the study arise from logistic feasibility and past experience with First in Human (FIH) studies in oncology and are not driven by statistical considerations. It is expected that approximately 277 patients will need to be enrolled to achieve the objectives of the study.

Due to the dynamic nature of the Bayesian allocation procedure, the sample size of the TITE-CRM approach cannot be determined in advance. The maximum sample size is set as 45 in order to have a reliable and accurate estimate of the MTD based on simulation results. Based on probability theory, a sample size of 45 will ensure the estimates of any binary variable (eg, objective response rate) have a 95% confidence interval (CI) of width <0.30 . A sample size of 45 also enables detection of any unexpected toxicity that occurs at 5% rate (in a non-dose-dependent fashion) with a probability of 0.90, and that occurs at 10% rate with a probability of 0.99.

A stopping rule will also be implemented if:

- Maximum sample size ($N=45$) is reached; or
- 9 DLT-evaluable patients have been treated at the estimated MTD; or
- all doses appear to be overly toxic and the MTD cannot be determined in the current trial.

Portion A expansion cohorts include patients with solid tumors of interest who progressed after treatment with an immune checkpoint inhibitor (anti-CTLA-4, anti-PD-1/PD-L1). The target sample size is approximately 20 patients with advanced melanoma at each tested dose (0.24 mg/kg, 0.6 mg/kg, 1.2 mg/kg) and approximately 20 patients, including other tumor types. With 20 patients with advanced melanoma, the maximum standard error of the ORR is 0.11.

Portion B expansion cohorts include approximately 80 patients with FL refractory to rituximab and to an alkylating agent at either 1.2 mg/kg or 0.24 mg/kg of PF-05082566. With 80 patients, the maximum standard error of the ORR is 0.06.

5.1.2. Decision Rules Using the TITE-CRM Method

A number of alternative designs have been proposed to the standard 3+3 design for Phase I dose escalation trials that improve its accuracy, efficiency and statistical validity, including the continual reassessment method (CRM) (O'Quigley et al., 1990), and its variants.

Delayed-onset toxicities are a particular challenge for phase I trials of combination therapies (Muler et al., 2004). Most of the available dose-escalation designs, including the 3+3 design, the up-and-down designs and the CRM design, require all patients to have completed a fixed observation period for toxicity (eg, 1-2 cycles of the experiment regimen, or 6-8 weeks after start of treatment) before additional cohorts of patients can be enrolled. Thus, trial accrual is subject to opening and closing which may pose logistical risk on the success and completion of the study. In addition, patients who are either lost to follow-up or die of events unrelated to treatment are usually required to be replaced. Due to these reasons, the trial duration could be unacceptably long in case of prolonged observation window and unexpected high rate of patient drop-out.

The time-to-event continual reassessment method (TITE-CRM), a variant of the original CRM method, is open to accrual continually, and maintains other advantages of the CRM relative to the 3+3 design. Like CRM, TITE-CRM seeks to determine the target MTD dose, defined as the dose most closely identified with the target rate, which is the largest acceptable DLT rate determined by the investigators based on the relative costs and benefits of the treatment.

TITE-CRM is to be implemented as described by Cheung et al. (2000) and Huang et al. (2014) for the dose escalation of PF-05082566. PF-05082566 will be administered IV at escalating doses of 0.60, 1.2, 2.4, 5 mg/kg as a single agent in Portion A (the standard 3+3 method is used for doses up to 0.30 mg/kg), and at escalating doses of 0.03, 0.06, 0.12, 0.18, 0.24, 0.30, 0.60, 1.2, 2.4, 5 mg/kg given once every 4 weeks in Portion B in combination with rituximab, which will be administered at a fixed dose of 375 mg/m², once per week for 4 weeks total (Cycle 1). If 5 mg/kg of PF-05082566 is well tolerated, the sponsor may investigate the 10 mg/kg level for the estimation of the MTD. The following dose levels are available for the dose ranges bracketed between 0.6 and 5 mg/kg based on the TITE-CRM indicated dose reduction from the next highest planned dose level: 0.45, 0.9, 1.8, 3.6, and 7.5 mg/kg). However, they will not be tested if a dose reduction is not recommended by the statistical model. In addition, these intermediate dose levels may be used for dose escalation if one dose limiting toxicity is observed at the preceding regular dose level.

We define the MTD to be the highest dose that is associated with a DLT rate $\leq 25\%$. A power function modeling DLT rate at each dose d_i ($i=1, \dots, 14$) expressed as $\Pr(\text{DLT} | d_i) = F_i(\beta)$ will be used:

[figure not shown]
$$F_i(\beta) = p_i^{\exp(\beta)}$$

where p_i is the prior estimate of DLT rate at dose level d_i , and $p_1 \leq p_2 \leq \dots \leq p_{14}$. These estimates will be projected based on the Portion A single-agent PF-05082566 safety profile in the first 3 dose levels, together with the pre-clinical animal data. β is an unknown single

parameter modeling the dose-toxicity relationship, with prior distribution $N(0, \sigma_0^2)$, where σ_0 is the standard deviation of the normal prior distribution with mean=0. At the beginning of the trial, the initial prior value of β is set as 0, the prior mean, which gives a prior dose-toxicity model of $F_i(\beta) = p_i$ based on the power function.

In the Bayesian paradigm, the prior distribution $N(0, \sigma_0^2)$ expresses the researchers' belief in the quality of the initial estimates p_i . The smaller the standard deviation σ_0 , the more confidence researchers have in the precision of p_i and vice versa. As the trial progresses, this prior distribution is combined mathematically with the observed data to yield the posterior distribution of the parameter β (the posterior mean of β will be calculated to model the dose-toxicity relationship). The prior distribution determines how responsive TITE-CRM is to the accumulated data. With a small σ_0 upfront, the posterior toxicity probability estimates remain close to the prior estimates unless significantly discrepant data otherwise occur; with a large σ_0 , the model will tend to be more immediately responsive to data. In our trial, we set $\sigma_0=0.97$, which provides a reasonably flat prior distribution of β , with 95% Bayesian credible interval of $\exp(\beta) : [0.15, 6.67]$, sufficiently wide to cover a wide spectrum of dose-toxicity scenarios. [Figure 3](#) illustrates the dose-toxicity curve with 95% upper and lower bounds when the initial prior estimates p_i are (1.4e-05, 1.4e-04, 9.0e-04, 3.8e-03, 0.01, 0.03, 0.06, 0.11, 0.17, 0.25, 0.33, 0.42, 0.50, 0.58).

Figure 3. Example Plot of Prior Dose Toxicity Curve

In the trial conduct, the first 3 patients will be treated at the lowest dose level. For each subsequent patient eligible for enrollment, the probability of DLT is estimated for each level based on all the collected data from all treated patients up to that time and the prior expectations of toxicity, and the patient is assigned to the currently estimated MTD, defined as the dose having an estimated probability of DLT closest to but not greater than the target rate (25%). The probabilities of toxicity are estimated based on the Bayesian power model with prior distribution of the parameter to learn about the overall dose-toxicity relationship. Patients' DLT data will be reported in real time to the study statistician who will estimate the MTD before the next enrolled patient is treated.

In the TITE-CRM paradigm, patients who have enrolled in the trial but have not experienced DLT will be included in the probability calculation with a weight equal to the proportion of the 8-week (2 cycles of PF-05082566) DLT observation period the patients have completed (however the weight function may be modified if safety data suggest different weight (toxicity) patterns in Cycle 1 and Cycle 2 of PF-05082566, or an adaptive weight function if ongoing safety data suggest different toxicity patterns in Cycle 1 and Cycle 2 of PF-05082566); patients who experience DLT or complete the observation period without DLT will be assigned full weight (=1).

5.2. General Methods

As described in [Section 3.7.1](#), in this study ‘**treatment group**’ refers to one of the following:

- PF-05082566 0.006 mg/kg q4wks;
- PF-05082566 0.03 mg/kg q4wks;
- PF-05082566 0.06 mg/kg q4wks;
- PF-05082566 0.12 mg/kg q4wks;
- PF-05082566 0.18 mg/kg q4wks;
- PF-05082566 0.24 mg/kg q4wks;
- PF-05082566 0.3 mg/kg q4wks;
- PF-05082566 0.6 mg/kg q4wks;
- PF-05082566 1.2 mg/kg q4wks;
- PF-05082566 2.4 mg/kg q4wks;
- PF-05082566 5 mg/kg q4wks;
- PF-05082566 10 mg/kg q4wks;
- PF-05082566 0.03 mg/kg q4wks + rituximab 375 mg/m² q1wk x4;
- PF-05082566 0.06 mg/kg q4wks + rituximab 375 mg/m² q1wk x4;
- PF-05082566 0.12 mg/kg q4wks + rituximab 375 mg/m² q1wk x4;
- PF-05082566 0.18 mg/kg q4wks + rituximab 375 mg/m² q1wk x4;
- PF-05082566 0.24 mg/kg q4wks + rituximab 375 mg/m² q1wk x4;
- PF-05082566 0.3 mg/kg q4wks + rituximab 375 mg/m² q1wk x4;
- PF-05082566 0.6 mg/kg q4wks + rituximab 375 mg/m² q1wk x4;
- PF-05082566 1.2 mg/kg q4wks + rituximab 375 mg/m² q1wk x4;
- PF-05082566 2.4 mg/kg q4wks + rituximab 375 mg/m² q1wk x4;
- PF-05082566 5 mg/kg q4wks + rituximab 375 mg/m² q1wk x4;
- PF-05082566 10 mg/kg q4wks + rituximab 375 mg/m² q1wk x4.

Baseline characteristics, disposition and efficacy data will be summarized based on the FAS by treatment group.

DLTs will be summarized based on the DLT-evaluable set by treatment group.

Other safety data, exposure data, concomitant medications and non-drug treatments will be summarized based on the safety analysis set by treatment group.

CCI

PK data will be summarized based on the PK analysis set by treatment group.

CCI

CCI

CCI

Immunogenicity data will be summarized based on the immunogenicity analysis set by treatment group.

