6.1.2. Objective Response as Assessed by the Investigator (Expansion Cohorts)

6.1.2.1. Primary Analysis

Refer to [Section 6.2.2.1](#).

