6.2.2. Efficacy Endpoints

The following analyses will be based on the FAS by treatment group. Assessment of response will be made using RECIST v1.1 for solid tumors and Cheson 2007 criteria for NHL.

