ORR by treatment group will be calculated along with the 2-sided 95% CI using the Clopper-Pearson method (exact CI for a binomial proportion as computed by default by the FREQ procedure using the EXACT option).

In addition, the frequency (number and percentage) of patients with confirmed BOR of CR, PR, SD, PD, non-CR/non-PD (applicable only to patients with non-measurable disease at baseline), and NE will be tabulated. Patients with BOR of NE will be summarized by reason for having NE status. The following reasons will be used:

- No baseline assessment.
- No post-baseline assessments due to death.
- No post-baseline assessments due to other reasons.
- All post-baseline assessments have overall response NE.
- New anti-cancer therapy started before first post-baseline assessment.
- SD or non-CR/non-PD of insufficient duration (<6 weeks after 'start date').
- PD too late (>12 weeks after 'start date').

Special and rare cases where BOR is NE due to both early SD or non-CR/non-PD and late PD will be classified as 'SD too early'.

BOR Based on Unconfirmed Responses for NHL:

- CR = one objective status of CR documented before progression.
- PR = one objective status of PR documented before progression (and not qualifying for CR).
- SD = at least one SD assessment (or better) ≥ 6 weeks after 'start date' and before progression (and not qualifying for CR or PR).
- PD = progression ≤ 12 weeks after 'start date' (and not qualifying for CR, PR, or SD).
- NE: all other cases.

An objective status of PR or SD cannot follow one of CR. SD can follow PR only in the rare case that tumor increases by less than 50% from the nadir, but enough that a previously documented 50% decrease from baseline no longer holds (see [Section 6.2.2.2](#) on details of tumor change).

OR is defined as BOR of CR or PR according to Cheson 2007 criteria.

Patients who do not have an on-treatment radiographic tumor assessment due to early progression, who receive anti-tumor therapies other than the study treatments prior to reaching a CR or PR, or who die, progress, or drop out for any reason prior to reaching a CR or PR will be counted as non-responders in the assessment of OR. Each patient will have an objective response status (0: no OR; 1: OR). OR rate (ORR) is the proportion of patients with OR in the analysis set.

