6.4. Subset Analyses

The number of patients expected in each treatment group is small and therefore no subset analyses are planned in this study.

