6.5.1.3. Disease Characteristics

Information on disease characteristics collected on ‘Primary Diagnosis’, RECIST, and IWGRC eCRF pages will be summarized overall and by treatment group. Summary statistics will be presented for the following.

From the ‘Primary Diagnosis’ eCRF page:

- Site of primary tumor;
- Primary diagnosis (summarize all categories collected in the ‘Primary Diagnosis’ eCRF page);
- Time since initial diagnosis to ‘start date’ (months), defined as (‘start date’ – date of initial diagnosis)/30.4375;
- For Portion A solid tumors: Time since diagnosis of local/regional recurrence of disease (months), defined as (‘start date’ – date of diagnosis of local/regional recurrence of disease)/30.4375.

From the RECIST tumor assessment eCRF page:

- Measurable disease (lesions) at baseline (Yes, No);
- Involved tumor sites at baseline.

From the IWGRC tumor assessment eCRF page:

- Involved tumor sites at baseline.

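### The primary expansion ORR is tabulated by dose only, so no stated analysis gives the melanoma ORR at 0.24 or 1.2 mg/kg, or the FL ORR at 1.2 mg/kg plus rituximab

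*SAP*

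**What the plan says.** SAP 3.7.1 and 5.2 list 23 treatment groups: 12 single-agent doses and 11 doses with rituximab. None carries a tumour type, a cohort name or an escalation/expansion label. SAP 5.2 applies the list to efficacy: "Baseline characteristics, disposition and efficacy data will be summarized based on the FAS by treatment group".

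SAP 6.1.2, headed as the expansion-cohort primary analysis, contains only a cross-reference to 6.2.2.1. SAP 6.2.2 opens with "The following analyses will be based on the FAS by treatment group", and 6.2.2.1 then says "ORR by treatment group will be calculated along with the 2-sided 95% CI using the Clopper-Pearson method", once for solid tumours and again for NHL. SAP 6.4 adds: "The number of patients expected in each treatment group is small and therefore no subset analyses are planned in this study".

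The precision statements in SAP 5.1.1 refer to narrower populations: "With 20 patients with advanced melanoma, the maximum standard error of the ORR is 0.11" and, for FL, "With 80 patients, the maximum standard error of the ORR is 0.06". The confidence-interval tables in protocol 9.3 are likewise labelled for advanced melanoma and for FL refractory to rituximab.

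Tumour type does appear elsewhere. Under SAP 6.5.1.3 the data from the primary diagnosis "eCRF pages will be summarized overall and by treatment group", and protocol 9.4 puts tumour type in the patient-level response listings.

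**The concern.** The expansion cohorts are not uniform in histology across doses. Protocol 4.1 admits melanoma, RCC, NSCLC and SCCHN to the Portion A expansion, and FL or DLBCL to Portion B. Table 5 footnote 19 gives the non-randomised cohorts only 0.24 or 1.2 mg/kg, and the randomised cohort is melanoma only. At the two outer single-agent doses, therefore, the tabulated ORR covers melanoma and other tumours together; among expansion patients at 0.6 mg/kg it covers melanoma alone. At 1.2 mg/kg plus rituximab it covers FL and DLBCL together.

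Objective response is the primary expansion endpoint (protocol 2.2.4), and these cohorts exist to support RP2D selection (protocol 1.4 and 3.3.1). A reader comparing ORR across the three single-agent doses would be comparing different case mixes. If a melanoma-only or FL-only rate is wanted later, it becomes a post hoc choice at odds with SAP 6.4. No hypothesis test is planned, so the issue is what is estimated and how it is read, not error rates.

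**Working it through.** **1. The plan's own precision figures.** Maximum SE = √(0.25/n).
- n = 20: 0.112, stated as 0.11.
- n = 80: 0.056, stated as 0.06.

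Both reproduce. Protocol 9.3's Clopper-Pearson interval for 4/20 (5.7 to 43.7%) also reproduces.

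**2. Who is in each expansion dose group.** I take the heading of SAP 6.1.2 as limiting the primary ORR to expansion patients, although 6.2.2.1 does not repeat that limit.
- Protocol 3.1.1: 34 patients treated at 0.24 or 1.2 mg/kg, 20 of them with melanoma, so 34 − 20 = 14 with other tumours.
- Protocol 3.1.1: about 40 further melanoma patients randomised 2:1:1, giving about 20 at 0.6, 10 at 0.24 and 10 at 1.2 mg/kg.
- Outer doses combined: 20 + 20 = 40 melanoma and 14 other, so 14/54 = 26% other. If the roughly 20 patients that protocol 9.3 describes as including other tumour types were all non-melanoma, the share would be 20/60 = 33%.
- 0.6 mg/kg: 0 of about 20.
- 1.2 mg/kg plus rituximab, with 4 DLBCL patients (protocol 3.1.2): 4/84 = 4.8% if FL-3 uses this dose (20 + 60 FL), or 4/24 = 16.7% if it does not (20 FL).

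**3. Would reporting randomised patients separately supply the figure?** That table would be melanoma only, but with about 10 patients at each outer dose: √(0.25/10) = 0.158, not 0.11. No text says that ORR is split this way.

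**4. Size of the shift in Portion A.** Assumptions, not given in the documents: melanoma ORR 20% at every dose; 20 melanoma patients per dose; k other tumours at each outer dose, with k = 14/2 = 7 or 20/2 = 10; other-tumour ORR q. Expected outer-dose ORR = (4 + kq)/(20 + k). The last two columns give the probability that 0.6 mg/kg shows the highest ORR of the three doses (exact binomial convolution, ties split equally). With melanoma only it is 0.333.

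| q | Expected ORR, k = 7 | Expected ORR, k = 10 | P(0.6 highest), k = 7 | P(0.6 highest), k = 10 |
|---|---|---|---|---|
| 0 | 14.8% | 13.3% | 0.568 | 0.614 |
| 0.1 | 17.4% | 16.7% | 0.455 | 0.473 |
| 0.2 | 20.0% | 20.0% | 0.354 | 0.347 |
| 0.3 | 22.6% | 23.3% | 0.269 | 0.243 |
| 0.4 | 25.2% | 26.7% | 0.199 | 0.161 |

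With q = 0.2 the probability is slightly above one third only because the outer groups are larger and so less variable.

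**5. Size of the shift in Portion B.** Assume an FL ORR of 50% and no DLBCL response.
- 40/80 = 50.0% (38.6 to 61.4%) becomes 40/84 = 47.6% (36.6 to 58.8%).
- If FL-3 uses the other dose, 10/20 = 50.0% (27.2 to 72.8%) becomes 10/24 = 41.7% (22.1 to 63.4%).

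**The case against.** The primary expansion objectives name neither melanoma nor FL; they ask for the ORR of PF-05082566, alone or with rituximab. Both documents say the sample sizes are not statistically driven. On that view ORR by dose meets the objective, and the SE figures merely describe precision. This lowers the weight of the point but does not remove it: the plan still sets target numbers and precision for melanoma per dose and for refractory FL, and specifies no estimate for those populations at the affected doses.

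The listings show tumour type, and in groups this small a reader could count the responders by hand. That is true, but a listing is not a pre-specified rate with a confidence interval.

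The ranking probabilities describe no rule in the plan. Protocol 3.6 bases the RP2D on primary and secondary endpoints together, not on the highest ORR. This stands: the table shows only how far case mix alone can move the apparent ordering.

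Read literally, the treatment groups also take in escalation patients, so 0.6 mg/kg would not be melanoma only (protocol 1.4 reports a Merkel cell response there). That reading adds mixing and leaves the problem in place.

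Parts of both documents are blacked out, including SAP 6.3 and the end of protocol 9.4, so the conclusion covers visible text only. The primary analysis statements in SAP 6.1.2 and 6.2.2.1, and the statement in 6.4, are readable.

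The FL effect is minor if FL-3 uses 1.2 mg/kg. That stands.

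**Conclusion.** The concern holds and should be fixed. In the visible text, no stated analysis gives an ORR with confidence interval for melanoma at 0.24 or 1.2 mg/kg, or for FL at 1.2 mg/kg plus rituximab, although the plan quotes precision for those populations. About a quarter of the expansion patients at the two outer single-agent doses are non-melanoma, against none at 0.6 mg/kg. The resulting shift can go in either direction: roughly 7 points down to 7 points up under the assumptions of a 20% melanoma ORR, an even split of other tumours between the two doses, and an ORR of 0 to 40% in those tumours. This is small beside an interval of 5.7 to 43.7% for 4/20. The count of 14 other tumours is as of September 2016, and the composition rests on reading the primary ORR as restricted to expansion patients.

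**What to change.** In SAP 5.2, 6.1.2 and 6.2.2.1, state that the primary expansion ORR with its Clopper-Pearson interval uses expansion-cohort patients only, and report it:
- for melanoma by dose, once for randomised patients alone and once combined with non-randomised patients at the same dose;
- for rituximab-refractory FL by dose;
- for other solid tumours in a separate table, with the 4 DLBCL patients listed or tabulated separately.

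Amend SAP 6.4 so that it does not exclude these groupings.

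The combined melanoma rate pools randomised with non-randomised patients and may pool drug preparations: Table 10 assigns 25 mg/mL to the randomised cohort, and preparation varies between cohorts. Showing the randomised patients alone beside it makes that visible.

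The cost is SAP wording and table shells. Primary diagnosis is already collected, so no new data are needed. The downside is more tables with smaller cells.
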